9 SECURITY ASSESSMENT

9.1 Security endpoints

- Frequency of side effects;
- Frequency of serious side effects;
- Frequency of clinically significant changes in laboratory parameters and vital signs after infusion of the study drug;
- Dynamics of laboratory parameters.

9.2 Definitions concerning safety assessment.

Adverse event

Adverse event (AE) is any adverse change in the health of a patient or subject who has been administered a drug, regardless of the causal relationship with its use.

AE can be any adverse and unintentional change, symptom or disease, the time of occurrence of which does not exclude a causal relationship with the use of the drug, regardless of the presence or absence of a relationship with the use of the drug.

AEs may be abnormal laboratory parameters, first-time symptoms, or diseases that are related to the use of the drug, or if they existed before treatment of a condition whose severity or frequency increased after administration of the study drug.

Any medical condition present at the time of the patient's screening, but not deteriorating during the study, should not be recorded as an AE. However, if this medical condition worsens at any time during the study, it should be recorded as an AE.

Medical interventions, such as surgeries, diagnostic and treatment procedures, are not AEs, but they are interventions to treat the relevant medical condition and should be registered as a treatment for ANs.

Deviations from the norm of laboratory parameters

Any deviation from the norm of the laboratory indicator, which appeared for the first time, or the degree of severity, the frequency of which has increased compared to baseline, and meets at least one of the following criteria, must be recorded as AE:

- Requires medical intervention or diagnostic procedure;

- Leads to the cancellation of the study drug;
- Accompanied by complaints or symptoms, or causes them;
- Considered by the researcher as "clinically significant".

If there is any doubt as to whether a clinical event is an AE, it should be recorded as an AE.

Adverse reaction

Adverse reaction (AR) is an adverse reaction of the body associated with the use of a medicinal product (study drug), which implies the presence of at least a possible relationship with the use of a suspected drug (study drug).

During the study period, the investigator or study staff should conduct surveys and record information on adverse events / reactions as defined in this section of the protocol.

Unforeseen adverse reaction

Unforeseen AR - adverse reaction, nature, severity or outcome of which does not correspond to the information contained in the general characteristics of the medicinal product (instructions for medical use) or in the researcher's brochure (for unregistered medicinal product).

| Bioven | Page 62 |
|----------------------------|--------------------------------|
| Trial Code: 2021-BV-ITP-BP | Version 1.4 from July 03, 2023 |

Serious adverse event

Serious adverse event (SAE)- Adverse medical event that leads to death, threatens life, requires hospitalization or continuation of hospitalization, leads to permanent or severe disability or incapacity, congenital anomalies or malformations, requires medical intervention to prevent the development of these conditions.

Page 62

Death- is usually the result of the underlying clinical phenomenon that causes it. Therefore, the cause of death should not be considered serious. The only exception is "sudden death", when its causes have been established. In this case, "sudden death" should be considered AE, the reason for its "seriousness" - its "lethality".

Threat to life- the term "threat to life" is defined as an AE during which there was a threat to the patient's life. This does not mean any AE that can hypothetically lead to death in the case of its increased complexity.

Hospitalization- any adverse event leading to hospitalization or continuation of hospitalization will automatically be considered serious if it does not meet any of the non-inclusion criteria listed below:

hospitalization lasts less than 12 hours or hospitalization is planned in advance (it is an optional or planned operation, which was agreed upon before the start of this study).

Disability is defined as a significant impairment of a person's ability to perform daily functions, such as a congenital anomaly / malformation.

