9.6. Table 2. The severity of NOT according to NCI CTCAE (version 5.0)

Daily activity (ADL):

* Social daily activities (SDA) include cooking, buying food or clothing, using the phone, handling money, etc.

** Self-care (SC) includes taking a bath, dressing and undressing, eating alone, using the toilet, taking medication and not being bedridden.

The terms "serious" and "severe" are not synonymous. Severe AE (Grade 3 or 4) should not always be considered serious. For example, leukocyte counts between 1000 and 2000 / mm3 should be considered grade 3 (severe), but such may not be considered severe. The benchmark for submitting information to regulators is the severity (not the expressiveness) of the AE.

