9.8. Categories of consequences of AE and their definitions

Measures taken:

- Without treatment;
- □ Cancellation of the suspected drug;
- □ Reducing the dose of the suspected drug;
- □ Cancellation of concomitant treatment;
- \Box Use of drug therapy;
- □ Non-drug therapy (including surgery).

The phenomenon passed without consequences -there are no symptoms, and the patient is not treated to eliminate this AR.

Stabilization of the state -the result of AR is classified as stabilization of the state according to the researcher.

The phenomenon passed with consequences -the phenomenon was curtailed, but its consequences remained; as a result of AR the patient has a temporary or permanent disability / incapacity; any AR that have passed with consequences are classified as serious AR.

The phenomenon has not yet passed -symptoms persist.

Death of the patient.

The result is unknown.

| Bioven | Page 66 |
|----------------------------|--------------------------------|
| Trial Code: 2021-BV-ITP-BP | Version 1.4 from July 03, 2023 |

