9.9. Reports of SAE

In the case of any SAE, the Study Sponsor must be notified within 24 hours of the researcher first learning about the SAE. During the development of SAE, the researcher fills in the SAE registration form and determines whether it is associated with the study drug and sends by fax or e-mail the completed form to the Sponsor of the study. The original SAE form and the fax confirmation letter must be kept. The fact of SAE should be recorded in the IRF. The sponsor has the right to urgently request from the researcher additional information about SAE for reporting to health authorities.

After the initial urgent notification, a detailed written notification must be submitted as soon as possible. Primary and subsequent reports should identify the subjects of the study by the unique code assigned to them, and not by the names of the subjects, personal identification numbers and (or) addresses.

In case of hospitalization of the patient in connection with the development of SAE, it is necessary to send as soon as possible fax or e-mail to the Sponsor of the study a copy of the hospital discharge.

The sponsor of the study or his authorized representative is responsible for notifying by telephone or fax of unforeseen or life-threatening SAEs related to the use of the study drug (in the form of urgent reports) to the relevant authorities and competent authorities within 7 calendar days obtaining information about SAE. The sponsor of the study drug to the appropriate authorities, researchers and the local ethics committee by providing a written safety report within 15 calendar days of receiving the information about SAE.

In Ukraine, the sponsor shall immediately register and within 7 calendar days from the moment he became aware of it, inform the SEC of the Ministry of Health of Ukraine and the Ethics Commission of all suspected unforeseen serious adverse reactions to the investigational medicinal product that resulted in death or threat for the life of the subject. Additional information on this subject is provided by the SEC of the Ministry of Health of Ukraine and the Ethics Commission within the next 8 calendar days. The notification of a suspected unforeseen serious adverse reaction must be made in accordance with the order of the Ministry of Health of Ukraine $N_{\rm D}$ 690 of 23.09.2009, as amended.

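### Section 9.2 contradicts itself on whether the event behind a death is serious, so a fatal event could be left unclassified as an SAE on the ground of death

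*Combined protocol and SAP*

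**What the plan says.** Section 9.2, under the serious adverse event definition, describes an SAE as: "Adverse medical event that leads to death, threatens life, requires hospitalization or continuation of hospitalization", followed by disability, congenital anomaly and events needing intervention to prevent these. Death is the first criterion.

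The next paragraph, on death, observes that death usually results from an underlying clinical event and concludes: "Therefore, the cause of death should not be considered serious". It adds: "The only exception is 'sudden death', when its causes have been established". In that case sudden death is the AE, and it is serious because it was lethal.

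Section 9.9 makes SAE status the trigger for reporting: "In the case of any SAE, the Study Sponsor must be notified within 24 hours of the researcher first learning about the SAE". The sponsor's expedited reports in 9.9 also start from SAEs or serious reactions. SAE frequency is one of the two safety endpoints listed in the synopsis and at the end of 8.2.

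Section 9.6 warns: "The terms 'serious' and 'severe' are not synonymous". It then closes with: "The benchmark for submitting information to regulators is the severity (not the expressiveness) of the AE". Section 9.5, just before it, uses severity and expressiveness as two names for one concept, the CTCAE grade.

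**The concern.** The same fatal event is serious under the main definition and not serious under the death paragraph. The death paragraph is the more specific text, so a site coding a fatal case is likely to turn to it. The exception makes matters worse. If the cause of a sudden death is known, that cause is the event to record. Sudden death is needed as the recorded event when no cause is known, and that is the case the exception leaves out.

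Seriousness carries several duties in this plan:
- the 24-hour notice and the sponsor's expedited reports (9.9);
- the SAE-frequency endpoint and its tabulation (8.2, 10.3.4);
- the sponsor's grounds for stopping the study, which include drug-related SAE data (6.5.14);
- the handling of events between screening and first dose, which go only into the medical history if they are not SAEs (9.3).

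The study plans 8 to 20 centres in two countries for 40 patients, an average of 2 to 5 patients per centre. A single site will have little experience against which to notice a faulty rule.

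**Working it through.** No stated figure depends on this point, so the main check is a comparison of the rules.

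**Step 1: apply 9.2 to two cases.**

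| Case | Main SAE definition | Death paragraph | Other 9.2 criteria |
|---|---|---|---|
| Fatal event of known cause, e.g. pulmonary embolism | Serious (leads to death) | Not serious | Threat to life normally met; hospitalization often met, but not for a stay under 12 hours |
| Sudden death, cause not established | Serious (leads to death) | Outside the exception | No underlying event identified to which they could be applied |

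Both rows conflict between columns two and three. The fourth column usually rescues the first case. In the second case only the main definition remains.

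**Step 2: does 9.9 resolve the conflict?** Only in part. Its rule for Ukraine names reactions that were fatal or life-threatening, but it still requires the reaction to be serious, so it inherits the question from 9.2.

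**Step 3: does the 9.6 sentence on regulators lose fatal events?** No. Section 9.5 grades death associated with an AE as Severity 5, the top grade, so even a trigger based literally on severity would capture it. The fault is one of terms: 9.5 equates two words that 9.6 then opposes.

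**Step 4: scale, as illustration only.** Inputs: N = 40 (synopsis and 4.1) or N = 36 (10.2). The intervals are exact (Clopper-Pearson) 95%. For zero events the upper limit is 1 − 0.025^(1/N).
- N = 40: 1/40 = 2.5% (0.06% to 13.16%). If that event is not classified, 0/40 = 0%, with upper limit 1 − 0.025^(1/40) = 8.81%.
- N = 36: 1/36 = 2.78% (0.07% to 14.53%). If not classified, 0/36 = 0%, with upper limit 1 − 0.025^(1/36) = 9.74%.

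Section 2.1 cites 0.02 to 0.04 fatal bleeds per adult patient-year. Over 28 days, 40 patients give 40 × 28/365 = 3.07 patient-years, so 3.07 × 0.02 = 0.06 to 3.07 × 0.04 = 0.12 fatal bleeds are expected. This counts fatal bleeds, not misclassified ones. The number lost would be smaller by the unknown chance that a site misapplies the paragraph.

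**The case against.** The strongest reply is that a fatal event would rarely escape. The main definition still names death. Section 9.2 separately makes an event serious if the patient's life was under threat during it, or if it led to or prolonged hospitalization. Section 9.3 requires all AEs to be registered whatever their severity or cause, 9.8 lists death as an outcome, and 9.9 refers to a death notification with further reports on request. Omission therefore needs a site to let one sentence override the rest. This stands, and it limits the point to a possible result of conflicting text. It does not remove the contradiction, since those routes ask the site to set aside an explicit sentence about death.

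A second reply is that the document is a translation and these sentences are language faults. That is plausible, both for the exception (perhaps a lost negative) and for the 9.6 sentence, which follows directly on the distinction between serious and severe. But the English text of version 1.4 is what is under review, and it needs correcting whatever the origin of the fault.

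A reader might also infer that reporting to regulators is tied to CTCAE grade, so that deaths drop out. The documents do not support this: the rules in 9.9 turn on SAE status, expectedness, relatedness and fatal or life-threatening outcome, and a fatal AE has the top grade in any case.

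A reader might further want 9.8 narrowed to match 9.2, because 9.8 says "as a result of AR the patient has a temporary or permanent disability / incapacity; any AR that have passed with consequences are classified as serious" while 9.2 asks for permanent or severe disability. The 9.8 wording widens capture and cannot lose a fatal event. Narrowing it could reduce the number of serious reactions captured.

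**Conclusion.** The contradiction within 9.2 is real and should be corrected. If a site follows the death paragraph, a fatal event may not be classed as an SAE on the ground of death, with effects on 24-hour notification and on the SAE-frequency endpoint. It would be too strong to say that the plan excludes fatal events or that a false report of no SAEs is likely, because the other criteria would usually catch them.

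The probability is low and cannot be estimated from the documents, and the consequence for reporting a death is serious. The intervals for zero and one event illustrate scale and apply to any missed SAE. They do not measure this defect. The primary endpoint, the sample size and the non-inferiority conclusion are unaffected. The 9.6 sentence is a secondary wording fault. The conclusion assumes that sites work from the English text as it stands, without separate SAE guidance that settles the matter.

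**What to change.** In 9.2, replace the death paragraph so that it agrees with the definition above it: death is an outcome; the event that led to death is recorded as the AE and is serious; where no cause is established, sudden death or death of unknown cause is recorded as the SAE.

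In 9.6, reword the closing sentence so that the benchmark for regulators is seriousness as defined in 9.2, not the severity grade, and use one term for each concept in 9.5 and 9.6. Leave 9.8 as it is for this purpose.

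The cost is a few sentences in section 9 and matching guidance on the SAE form. No visit, procedure or sample-size change follows.

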9.3 Detection and registration of AE

Detection and registration of SAE begins from the moment of signing the informed consent and lasts until the end of the patient's participation in the study.

Detection and registration of AE begins with the introduction of the drug and lasts until the end of the patient's participation in the study.

AE that occur between screening and administration of a drug, but does not considered as a SAE should be recorded as a medical history.

All AEs arising from the administration of the drug reported by the patient or detected during observation, physical examination and other diagnostic procedures must be registered in the AE Reporting Form attached to the Individual Registration Card.

Laboratory parameters will be evaluated during screening and throughout the study.

Information on any AE observed during the study period, from the first use of the study drug to the end of its use, is recorded in the patient's medical history / outpatient card and in the IRF registration section. All AEs are subject to registration, regardless of the severity or the presence of a causal relationship with the investigational medicinal product.

As AE should be classified:

- exacerbation of previous diseases;
- · increase in the frequency or intensity of diseases or episodic phenomena observed earlier:
- diseases detected or diagnosed after the start of the study drug, even if it is possible before the patient's participation in the study;
- long-term, persistent disease or symptoms that were in the initial stage, the severity of which increased after the start of the patient's participation in the study;

- the appearance of new signs or an increase in the severity of the signs and symptoms of diabetes mellitus, which require urgent therapy, hospitalization, surgery and / or other intervention;
- clinically significant abnormalities detected by laboratory diagnostics or other examinations after the start of the study drug or available at baseline, the severity of which increased on the background of the study drug.

AS a AE should not be classified:

- 1. diseases or pathologies detected or diagnosed before the use of the investigational medicinal product, the severity of which does not increase;
- 2. situations in which there is no medically unfavorable event (for example, hospitalization for the planned surgery);
- overdose of any of the studied drugs or concomitant drugs without unwanted signs or symptoms;
- 4. any clinically significant deviation of the laboratory indicator from the norm, detected before the first use of the study drug;
- 5. signs and symptoms observed during the study, which are associated with insufficient effectiveness of treatment.

The study will monitor the occurrence of any adverse events (AE). Table 1 presents the tolerance assessment scale.

| Category | Category description |
|----------------|--|
| Good | At objective inspection in dynamics any pathological changes or clinically significant deviations does not find, data of laboratory inspection do not change reliably and do not go out of norm, the patient does not feel the side reactions. |
| Satisfactory | At objective inspection in dynamics insignificant changes which have temporary character and do not demand change of the scheme of treatment and carrying out additional medical actions come to light. and / or laboratory test data deviate slightly from normal. and / or there are minor side effects that do not cause serious problems to the patient and do not require discontinuation of the drug |
| Unsatisfactory | At objective inspection in dynamics the pathological changes demanding drug cancellation and carrying out additional medical actions come to light. and / or laboratory test data undergo clinically significant negative changes, which entails the need for additional examination and interpretation of data and / or there is an undesirable side effect that has a significant negative impact on the patient's condition, requiring discontinuation of the drug and the use of additional medical measures |

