5. SELECTION AND EXCLUSION OF RESEARCH SUBJECTS

5.1. Inclusion criteria

- Signed Informed consent form to participate in the study;
- Men and women aged 18-65 years;
- Significantly confirmed chronic primary ITP (at last 12 months after diagnosis);
- The general analysis of blood should be normal except for the isolated thrombocytopenia. Patients with low hemoglobin (but above 90 g / l) may be included if there are symptoms of bleeding;
- In case of diagnosis of bleeding symptoms, reticulocyte counts should be monitored;
- Platelet count $< 30 \times 109/L$;
- If the patient is taking corticosteroids, the treatment regimen / dose should be stable (at least 2 weeks before screening);
- Negative pregnancy test (in women of reproductive age), willingness to use reliable methods of contraception throughout the study;
- The results of physical, instrumental and laboratory examination of patients within the norm and deviations are considered by the investigator as clinically insignificant;
- The ability, according to the investigator, to follow all the requirements of the study protocol.

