10.3.4. Analysis of safety and tolerability parameters

A) Data on AE/AR, Indicators of descriptive statistics (frequency and part in percent) and a list of adverse reactions according to the MeDRA classification

B) Data on SAE. Indicators of descriptive statistics (frequency and part in percent) and a list of adverse reactions according to the MeDRA classification.

Clinically significant deviations in indicators characterizing the safety and tolerability of the drug: Laboratory results of general blood analysis, biochemical blood analysis and general urinalysis; the result of determining the Coombs test and signs of hemolysis.

Provide descriptive statistics for these indicators (n, arithmetic mean, median, standard deviation, minimum and maximum value) for all visits.

To evaluate the dynamics of laboratory indicators, we used the Student's test for paired data or the Wilcoxon signed rank test, depending on the normality of the distribution of paired differences ["after" - "before"]. Create dichotomous variables with the categories "normal" and "abnormal", calculate the indicators of descriptive statistics (frequency and part in %) for these variables.

Measurement results of heart rate, blood pressure, respiratory rate, body temperature. Indicators of descriptive statistics (n, arithmetic mean, median, standard deviation, minimum and maximum value) for each visit in accordance with the patient examination scheme. Evaluate the trend of changing these parameters.

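### Item 4 of the section 9.3 exclusion list has no worsening condition, so read literally it keeps a worsened baseline laboratory abnormality out of the AE count, against 9.2 and the 9.3 inclusion list

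*Combined protocol and SAP*

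**What the plan says.** Four statements in section 9 bear on a laboratory value that is already abnormal before dosing and then gets worse.

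- Section 9.2, deviations of laboratory parameters: a deviation that is new, or whose severity or frequency "has increased compared to baseline, and meets at least one of the following criteria, must be recorded as AE". The four criteria are a need for medical intervention or a diagnostic procedure, withdrawal of the drug, accompanying complaints or symptoms, or the investigator's judgement that it is clinically significant.
- Section 9.2, conditions present at screening: "if this medical condition worsens at any time during the study, it should be recorded as an AE".
- Section 9.3, list of what is to be classified as an AE: clinically significant laboratory abnormalities found after the start of the drug, or those "available at baseline, the severity of which increased on the background of the study drug".
- Section 9.3, list of what is not to be classified as an AE. Item 1 covers "diseases or pathologies detected or diagnosed before the use of the investigational medicinal product, the severity of which does not increase". Item 4 covers "any clinically significant deviation of the laboratory indicator from the norm, detected before the first use of the study drug".

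Section 9.2 also says that a clinical event of doubtful status should be recorded. AE frequency is a safety endpoint in the synopsis and in sections 8.2 and 9.1.

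**The concern.** Item 1 and item 4 do the same job, one for diseases and the other for laboratory values, but only item 1 is limited to cases that do not get worse. Item 4 says any deviation. An investigator who looks up a worsened baseline laboratory abnormality finds it in both lists: an AE in the first, not an AE in the second.

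The case is foreseeable. Section 5.1 states: "Patients with low hemoglobin (but above 90 g / l) may be included if there are symptoms of bleeding". Section 2.4 names hemolysis as a risk of the product. A patient who enters anaemic through the bleeding exception and then loses more hemoglobin is the obvious example.

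At stake is the reported AE frequency and its consistency across sites (5-15 in Ukraine and 3-5 in Turkey, per the synopsis). AE status also brings severity grading (9.5), causality assessment (9.7) and follow-up (9.4), so a non-serious event left out of the AE form could miss those steps too.

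**Working it through.** The plan states no figure on this point, so there is none to reproduce. The check is a comparison of the passages, followed by one line of arithmetic for scale.

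**Step 1: one case against each rule.** Take, as an assumed illustration, hemoglobin of 95 g/L at screening in a bleeding patient, judged clinically significant, and 75 g/L on Day 7, also judged clinically significant.

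- 9.2 laboratory rule: severity has increased and the fourth criterion is met, so it is an AE. Without any of the four criteria, this rule would not require recording.
- 9.3 inclusion list: an abnormality present at baseline has worsened on the drug, so it is an AE.
- 9.3 exclusion item 4, read literally: hemoglobin was already a clinically significant deviation before the first dose, so it is not an AE.
- 9.3 exclusion item 1, for contrast: its condition fails because severity increased, so it would not exclude a disease that followed this course.

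The conflict comes from the missing condition in item 4. With the condition that item 1 carries, all four rules agree.

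**Step 2: who can be affected.** Item 4 applies only to deviations that are clinically significant before dosing. Section 5.1 otherwise requires baseline laboratory results to be normal or their deviations to be judged clinically insignificant. That leaves mainly patients admitted through the low-hemoglobin exception whose value was judged clinically significant. The documents do not say how many there would be. Every patient also enters with a low platelet count, but a further fall there is arguably lack of effect, which item 5 of the same list deals with separately.

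**Step 3: what other outputs would show.**

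- Section 9.1 has a separate endpoint for the frequency of clinically significant laboratory changes after infusion. The fall would count there.
- Section 10.3.4 gives mean, median, standard deviation, minimum and maximum at all visits, a paired before-after test, and Coombs and hemolysis results. A value of 75 g/L could appear as the minimum and would contribute to the paired test.
- Section 10.3.4 also says "Create dichotomous variables with the categories" normal and abnormal. A patient abnormal before and after shows no change in that variable.

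**Step 4: scale.** Inputs: 40 patients (section 4.1) or 36 (section 10.2). If one patient's only AE is left out, the proportion of patients with an AE falls by 1/N:

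- 1/40 = 0.025, or 2.5 percentage points
- 1/36 = 0.0278, or 2.8 percentage points

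If that patient has any other recorded AE, the proportion of patients does not change and only the count of events falls by one.

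**The case against.** The best defence is that item 4 is limited by the time of detection. A Day 7 value was not detected before the first dose, so item 4 may only restate the rule earlier in 9.3 that AE registration starts with administration and that earlier non-serious events are medical history. On that reading it fits with the inclusion list, which addresses worsening expressly. The doubt rule in 9.2 then points a hesitant site towards recording. This may well be the intent, and it means that loss of the event is possible, not certain. It does not remove the conflict: item 1 needed an explicit condition to say this and item 4 has none, and a site that follows an express exclusion may see no doubt to resolve.

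A reader might infer more than the text supports, in four ways.

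- *That drug-induced hemolysis would be missed.* Item 4 concerns a laboratory indicator. Under 9.3, a disease diagnosed after the start of the drug is an AE, and section 9.4 says that a known diagnosis should be used as the AE term. Newly diagnosed hemolysis is therefore recorded in its own right.
- *That the fall would be hidden everywhere except in the group mean.* The 9.1 endpoint and the 10.3.4 minimum, paired test and Coombs/hemolysis results would still reflect it. Only the normal/abnormal variable is blind to it.
- *That every worsened laboratory value is an AE under 9.2.* One of the four criteria must also be met.
- *That each affected patient moves the AE rate by 2.5 or 2.8 points.* This holds only for the proportion of patients with an AE, and only where the omitted event is the sole one.

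**Conclusion.** Item 4 is wrong as written, and the error is minor. It is a stated classification rule that, taken literally, contradicts the 9.3 inclusion list and the 9.2 laboratory rule, and it can lead a site to leave a worsened baseline abnormality out of the AE frequency. The effect is confined to the AE tables and the AE handling that follows from them. The primary efficacy analysis and the sample size are untouched, and a fall that meets the SAE definition should still be reported.

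The size is at most 2.5 points (N = 40) or 2.8 points (N = 36) per patient, on three assumptions: the site reads item 4 literally, the pre-dose value was judged clinically significant, and the patient has no other AE. The documents give no number of such patients, so no total effect can be estimated. They do not support a claim that safety will be materially understated.

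**What to change.** Add to item 4 of the 9.3 exclusion list a condition parallel to the one in item 1: the exclusion applies only where neither the severity nor the frequency of the deviation increases after the first use of the study drug. State in the same place that worsening of a baseline laboratory deviation is handled by 9.2 and by the 9.3 inclusion list. Both references are needed, because 9.2 asks for one of four criteria and the inclusion list does not repeat them. Carry the same wording into the CRF completion instructions.

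The cost is one phrase and a cross-reference, with no new data, visits or tests. The reported AE rate may be slightly higher.
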